7.1.4 UNANTICIPATED (SERIOUS) ADVERSE DEVICE EFFECT (UADE)

Unanticipated adverse device effect means any serious adverse effect on health or safety or any life-threatening problem or death caused by, or associated with, a device, if that effect, problem, or death was not previously identified in nature, severity, or degree of incidence in the investigational plan or application (including a supplementary plan or application), or any other unanticipated serious problem associated with a device that relates to the rights, safety, or welfare of subjects.

Per the definition above, a UADE is a type of serious adverse event (SAE) that requires expedited reporting on the part of the sponsor. As a reminder, all SAEs regardless of relationship to device, drug or procedure are to be reported to Sponsor by the study investigator within 24 hours. Sponsor will assess each device related SAE to determine if anticipated based on prior identification within the investigational plan.

7.1.5 ASSESSING SEVERITY (INTENSITY)

Adverse events should be captured once on the CRF at the maximum severity reported.

The investigator will grade laboratory AEs and clinical AEs with respect to the following levels of severity as per Common Toxicity Criteria for Adverse Events (CTCAE) v 4.03 for applicable subject populations:

- Mild (Grade 1)
- Moderate (Grade 2)
- Severe (Grade 3)
- Potentially Life Threatening (Grade 4)

The investigator will grade injection site reactions in accordance with September 2007 FDA Guidance for Industry—Toxicity Grading Scale for Healthy Adult and Adolescent Volunteers Enrolled in Preventive Vaccine Clinical Trials.

7.1.6 CAUSAL RELATIONSHIP OF CLINICAL MATERIAL TO ADVERSE EVENTS

A causally related AE is one judged to have a reasonable possibility of a relationship to the administration of the IP and/or the investigational device. An AE may also be assessed as not

related to the IP and/or the investigational device. Because the investigator is knowledgeable about the subject (e.g., medical history, concomitant medications), administers the IP, and monitors the subject's response to the IP, the investigator is responsible for reporting adverse events and judging the relationship between the administration of the IP and device and a subsequent AE. The investigator is aware of the subject's clinical state and thus may be sensitive to distinctions between events due to the underlying disease process versus events that may be product related and may have observed the event. The Sponsor will assess the overall safety of the IP delivered by EP and determine whether to report expeditiously to the regulatory agencies.

Investigators should use their knowledge of the subject, the circumstances surrounding the event, available site and non-site laboratory and clinical records, and an evaluation of any potential alternative causes to determine whether or not an adverse event is considered to be related to the IP and/or the investigational device indicating "yes" or "no" accordingly. Causality should be assessed by the investigator as "yes, related" or "no, unrelated" by the following criteria:

- Yes there is a reasonable possibility that administration of the Study Treatment contributed to the event;
- No there is no reasonable possibility that administration of the Study Treatment contributed to the event and there are more likely causes.

The following guidance should also be taken into consideration:

- Temporal relationship of event to administration of IP and/or the investigational device;
- Course of the event, considering especially the effects of dose reduction, discontinuation of IP, or reintroduction of IP (where applicable);
- Known association of the event with the IP, EP or with similar treatments;
- Known association of the event with the disease under study;
- Presence of risk factors in the Study Subject or use of concomitant medications known to increase the occurrence of the event.

7.1.7 ABNORMAL LABORATORY VALUE

Laboratory abnormalities are usually not recorded as AEs or SAEs. However, laboratory abnormalities (e.g., serum chemistry, CBC, CPK, urinalysis) independent of the underlying medical condition that require medical or surgical intervention or lead to IP interruption or discontinuation must be recorded as an AE, or SAE, if applicable. In addition, laboratory or other abnormal assessments (e.g., electrocardiogram, x-rays, vital signs) that are associated with signs and/or symptoms must be recorded as an AE or SAE if they meet the definition of an AE (or SAE) as described in Section 7.1. If the laboratory abnormality is part of a syndrome, record the syndrome or diagnosis (e.g., anemia) not the laboratory result (e.g., decreased hemoglobin).

Any laboratory abnormality that is new in onset or worsened in severity or frequency from the baseline condition and meets one of the following criteria will be recorded as an AE:

- Requires therapeutic intervention or diagnostic tests
- Leads to discontinuation of study treatment
- Has accompanying or inducing symptoms or signs

• Is judged by the investigator as clinically significant

7.1.8 POST-STUDY REPORTING REQUIREMENTS

All AEs and SAEs including deaths, regardless of cause or relationship, must be reported for subjects on study (including any protocol-required post-treatment follow-up).

Investigators are not obligated to actively seek AEs or SAEs beyond the follow up period for subjects. However, if the investigator learns of an AE or SAE that occurs after the completion or termination visit and the event is deemed by the investigator to be related to the study treatment, he/she should promptly document and report the event to the study team and medical monitor.

7.1.9 PROCEDURES FOR DOCUMENTING PREGNANCY DURING STUDY

Subjects who are pregnant or expect to become pregnant during the course of the study up to 6 months following the last study treatment of investigational product will be excluded from participation in the study. Should a subject become pregnant after enrolling in the study, she will not be given any further study treatments. A Pregnancy Form will be completed by the site personnel and submitted to the sponsor study team and medical monitor within 24 hours after learning of the pregnancy. The investigator will also report this event to the IRB within 24 hours of becoming aware of the pregnancy. Sites must request the subject's permission to query pregnancy outcome and follow each subject to determine the outcome of the pregnancy. Results will be summarized in the clinical study report (CSR).

Subjects who become pregnant at any point during the study will continue to be followed for safety assessments without receiving further study treatment. Procedures that are contraindicated during pregnancy, including additional treatments, must not be performed. Investigators should use clinical judgment regarding subsequent study-related blood collection based on the presence or absence of anemia in each subject. Subjects who are not withdrawn will continue to be followed for safety assessments to study discharge per protocol.

All pregnancies that occur from the time of first study treatment through the follow up visits must be reported. The investigator will monitor the subject and follow the outcome of the pregnancy. If the end of the pregnancy occurs after the study has been completed, the outcome will be reported directly to the study team and the medical monitor.

7.2 METHODS AND TIMING OF THE COLLECTION AND RECORDING OF SAFETY DATA

Non-serious AEs and SAEs (and UADEs) will be collected for each subject from the time when informed consent is obtained through Week 88.

The sources of AEs cover:

- 1. The subject's response to questions about her health (a standard non-leading question such as 'How have you been feeling since your last visit?' is asked at each visit).
- 2. Symptoms spontaneously reported by the subject.

- Evaluations and examinations where the findings are assessed by the investigator to be clinically significant changes or abnormalities.
- Other information relating to the subject's health becoming known to the investigator (e.g. hospitalization).

All AEs will be reported on the appropriate CRF. Any SAE (or UADE) occurring during the course of the study must be reported to the sponsor within 24 hours of awareness.

7.3 SAFETY AND TOXICITY MANAGEMENT

The Medical Monitor will be responsible for the overall safety monitoring of the study. Safety assessments include the following:

- Incidence of all adverse events classified by system organ class (SOC), preferred term, severity, and relationship to study treatment
- Changes in safety laboratory parameters (e.g., hematology, serum chemistry, and urinalysis)
- Local and systemic injection site review; special attention will be paid to the examination of the injection site. Administration site reactions and the subject's complaints will be documented.

[figure not shown]
7.3.1 EVENTS REQUIRING EXPEDITED REPORTING

Events requiring expedited reporting (ERER) will be defined as related adverse events due to VGX-3100X/placebo delivered with CELLECTRA[™] 5PSP that meets any of the following criteria:

- Grade 3 or greater administration site erythema, and/or induration recorded ≥ 2 hours after Study Treatment
- Grade 4 or greater administration site pain, tenderness recorded ≥ 2 hours after Study Treatment
- Grade 3 or greater fever
- Grade 3 or greater systemic symptoms, including generalized pruritus

As per the Toxicity Grade for Healthy Adults and per CTCAE v 4.03. The most severe grade for that particular event is to be documented in the CRFs.

Sites will inform the Sponsor vial email and to designee vial phone or fax of any ERER within 24 hours to discuss whether further dosing should continue by contacting Inovio as follows.

7.3.2 STOPPING RULES (CRITERIA FOR PAUSING OF STUDY)

- If at any time during a study one-third (1/3) or more of the subjects experience an ERER, further enrollment and study treatment will be halted immediately until a thorough investigation has been conducted by the Medical Monitor, Principal Investigator for the trial, and the DSMB. Only the DSMB may review unblinded data in making their recommendation to the Sponsor regarding continuation of a trial.
- If any SAE (or potentially life-threatening AE), or death assessed as related to study treatment occurs, further enrollment and study treatment will be halted immediately until a thorough investigation has been conducted by the Medical Monitor, Principal Investigator for the trial, IRB (if applicable) and the DSMB.
- If three or more subjects in this study, experience the same Grade 3 or 4 adverse event, assessed as related to study treatment, further enrollment and study treatment will be halted immediately until a thorough investigation has been conducted by the Medical Monitor, Principal Investigator for the trial, and the DSMB.
- In the event of two identical, unexpected, Grade 4 toxicities, assessed as related to study treatment, further enrollment and study treatment will be halted immediately until a thorough investigation has been conducted by the Medical Monitor, Principal Investigator for the trial, IRB (if applicable) and the DSMB.

The sponsor or designee will notify all investigators and IRBs/EC (if required) regarding the outcome of any investigation stemming from a Study Pause.

Guidelines for assessing relatedness are detailed in Section 7.1.6.

8 STATISTICAL ANALYSIS PLAN

8.1 GENERAL CONSIDERATIONS

The statistical analysis of the data will be performed by Inovio Pharmaceuticals or its representative.

This is a two-arm, multi-center, placebo-controlled, blinded, and randomized clinical trial in subjects with a histologic diagnosis of cervical HSIL. The study's primary endpoint is binary: regression to CIN1/normal and clearance of HPV-16 and/or HPV-18 infection from cervical tissue based on tissue collected at Week 36. The primary hypothesis is that VGX-3100X will be superior to placebo regarding the proportion who achieve the primary endpoint. Secondary efficacy analyses involve regression to CIN1/normal, clearance of HPV-16 and/or HPV-18 infection from cervical tissue and non-progression of cervical lesions. Other secondary analyses concern safety and humoral and cellular immunological measures. Exploratory analyses concern tissue immunological measures, durability of clearance of HPV-16 and/or HPV-18 infection from cervical tissue, clearance of HPV-16 and/or HPV-18 infection from non-cervical tissue, effect of HLA type on efficacy, association of colposcopy, cytology, and virology and efficacy, and patient-reported outcomes.

8.2 RANDOMIZATION AND BLINDING

Subjects will be randomized (2 VGX-3100X:1 Placebo) in a stratified manner according to a) the degree of CIN observed in the biopsy specimens at screening (CIN2 vs. CIN3), b) BMI category (≤25 vs. >25 kg/m²), and c) age category (<25 years vs. ≥25 years). There will be no pre-determined number of subjects required to be randomized within each stratum. To ensure that milder CIN2 disease is not over-represented in the study, the percentage of subjects enrolled with CIN2 will not exceed 50% of the total enrolled.

The study is double-blinded.

8.3 SAMPLE SIZE/POWER

A sample of 165 subjects will be randomized to receive either 6 mg VGX-3100X or placebo IM followed by EP in a 2:1 ratio. This sample size provides 90% power to declare VGX-3100X superior to placebo, assuming the true proportion of subjects who achieve the primary endpoints is 40% and 15% for VGX-3100X and placebo, respectively, and assuming 90% evaluability from randomization. These assumptions are based on the mITT result from the Phase 2 study.

8.4 ANALYSES POPULATIONS

Analysis populations will include:

- The modified intention to treat (mITT) population includes all subjects who receive at least one dose of Study Treatment. Subjects in this sample will be grouped to treatment arms as randomized. Analysis of the mITT population will be primary for the analysis of efficacy in this study.
- The per-protocol (PP) population comprises subjects who receive all doses of Study Treatments and have no protocol violations. Subjects in this sample will be grouped to treatment arms as randomized. Analyses on the PP population will be considered supportive of the corresponding mITT population for the analysis of efficacy. Subjects excluded from the PP population will be identified and documented prior to unblinding of the study database.
- The safety analysis set includes all subjects who receive at least one does of Study Treatment. Subjects will be analyzed as to the treatment they received.

Subjects who do not complete the study will not be replaced.

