2.2 TREATMENT PLAN

The three dose regimen of VGX-3100 appeared to be safe and well tolerated in the Phase 2b study, therefore all eligible subjects who consent to participate in the Phase 3 study will receive the same three 6 mg doses of VGX-3100X or placebo administered in 1 mL IM (deltoid, preferred site, or anterolateral quadriceps, alternate site), each followed immediately by EP with the CELLECTRA™ 5PSP device. The first study treatment will be administered on Day 0, the second at Week 4, and the third (final) study treatment will be administered at Week 12 which is consistent with the Phase 2b study. The first study treatment will be given as soon as possible following confirmation of the cervical HSIL diagnosis and HPV-16/18 status but no more than 10 weeks following collection of the subject's biopsy specimen used for diagnosis by the PAC during screening, contemporaneous with the positive testing for HPV-16/18.

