6.13.1 ECTOCERVICAL BIOPSIES

Ectocervical biopsies are required at screening to confirm eligibility. If the criteria outlined in Table 5 or 6 are met, ectocervical biopsies may also be performed at Week 36 to provide tissue for histopathologic assessment of disease regression.

Biopsies should not be performed at any other visit unless there is suspicion of disease progression. Removal of additional tissue by biopsy before Week 36 will bias results toward improvement regardless of whether the subject is in the active or placebo group. The bias introduced will obviously be more significant for smaller lesions. For this reason, if biopsies are obtained prior to Week 36, the subject will be treated as a non-regressor. Subject safety is paramount in this study. Therefore, if at any time the investigator may suspect disease progression and the standard of medical care would be to perform an unscheduled biopsy prior to Week 36, then his or her medical judgment should prevail over the default "Schedule of Events", Table 1.

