6.13.2 UNSCHEDULED BIOPSIES

In the event unscheduled biopsy is performed prior to Week 36, subject will be considered as non-responder. The subject will discontinue further study treatment and continue in the study for safety follow-up visits. The subject will be managed according to standard of care and Investigator's judgement based on results of histological diagnosis from unscheduled biopsy Additional instructions for collecting ectocervical biopsies are detailed in Appendix C. All biopsy samples/excised tissue will be sent to the PAC for review.

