8.9 EFFICACY ANALYSES

The true treatment effect on the primary endpoint is $\delta = p_V - p_P$, where p_V and p_P denote the true population probabilities of the primary endpoint for VGX-3100X and Placebo, respectively. The primary hypothesis of superiority is:

$$H_0$$
: $\delta \leq 0$ vs. H_1 : $\delta > 0$.

A p-value for this hypothesis test and corresponding 95% confidence interval will be computed based on the method of Miettinen and Nurminen [27]. Superiority will be concluded if the one-sided p-value is <0.025 and the corresponding lower bound of the 95% CI exceeds zero.

The secondary efficacy endpoints will be analyzed in the same manner as the primary hypothesis, but without the hypothesis test p-values.

The histopathologic efficacy time frame is defined by those who have undergone a biopsy or surgical excision at any time starting from 14 days prior to the protocol-specified target date of Week 36. It also includes subjects who underwent early intervention prior to this time frame; these subjects are considered as failures for the efficacy endpoints. Table 13 provides details for the definition of the primary endpoint response.

Table 13. Definition of Primary Endpoint Responder and Non-Responder

Responder	Non-Responder
Subject with no histologic evidence of cervical	Subject with histologic evidence of cervical HSIL, AIS, cervical carcinoma at Week 36 evaluation
HSIL ^a at Week 36 evaluation and no evidence of HPV-16 or HPV-18 at Week 36	OR
AND	Subject with evidence of HPV-16 or HPV-18 at Week 36
Subject in which a cervical tissue sample was NOT obtained between collection of tissue to determine entry eligibility up to Week 36 primary endpoint visit	OR
	Subject in which an additional cervical tissue sample was obtained between collection of tissue to determine entry eligibility up to Week 36 primary endpoint visit

^a no evidence of HSIL is defined by histology as negative, squamous atypia, or LSIL

Exploratory analyses will examine the relationship between the primary efficacy endpoint and a) HLA results, b) colposcopy results, c) cytology results, and d) HPV results. As each of these results are categorical, relationships will be examined with contingency tables and logistic regression models which model the primary endpoint versus these results and treatment group as regressor variables.

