8.15 MISSING VALUES

Missing data will not be imputed or replaced, and calculations will be done on reported values.

A subject's regression outcome is missing if her CIN grade and HPV clearance at Week 36 cannot be determined. Any subject who had suspected disease progression before Week 36 will be considered a non-regressor regardless of the Week 36 result, even if missing.

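### A woman biopsied for suspected progression before dose 3 is a defined failure, yet the all-doses rule removes her from the supportive per-protocol analysis

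*Protocol*

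**What the plan says.** All references are to version 2.1 unless stated.

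- **Who is in PP (8.4).** "The per-protocol (PP) population comprises subjects who receive all doses of Study Treatments and have no protocol violations". Its role is stated next: "Analyses on the PP population will be considered supportive of the corresponding mITT population for the analysis of efficacy".
- **What an unscheduled biopsy does to the outcome (6.13.2).** "In the event unscheduled biopsy is performed prior to Week 36, subject will be considered as non-responder".
- **What it does to dosing (6.13.2).** "The subject will discontinue further study treatment and continue in the study for safety follow-up visits".
- **When such a biopsy may be taken (6.13.1).** "Biopsies should not be performed at any other visit unless there is suspicion of disease progression". The same section lets the investigator's judgement override the visit schedule in that case.
- **How early intervention is scored (8.9).** Women with an intervention before the Week 36 window are counted, and "these subjects are considered as failures for the efficacy endpoints".
- **How suspected progression is scored (8.15).** "Any subject who had suspected disease progression before Week 36 will be considered a non-regressor regardless of the Week 36 result, even if missing".
- **When dosing ends (2.2).** "the third (final) study treatment will be administered at Week 12".

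The modified intention-to-treat (mITT) population in 8.4, which carries the primary analysis in version 2.1, needs only one dose.

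**The concern.** Each rule is clear by itself. Together they mean that, for biopsies before dose 3, PP membership depends on the outcome. Take a woman who receives dose 1 and is biopsied at Week 6 because progression is suspected. Section 6.13.2 ends her dosing, so she can never meet the all-doses condition. She has broken no rule: 6.13.1 permits the biopsy and 6.13.2 dictates what follows. She is also a non-responder by definition. She therefore leaves both numerator and denominator of the PP response rate.

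A PP analysis is meant to show whether the primary result holds among women who followed the plan. Here it also conditions on not having failed before Week 12. Removing failures alone raises the response rate in any arm that loses them, and the treatment difference moves with the split of those losses between arms. Agreement between PP and the primary analysis would then say less than it appears to.

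**Working it through.** **Who is affected.** The first scheduled colposcopy after Day 0 is at Week 15 (6.13), three weeks after the last dose.

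- Biopsy before dose 3: dosing stops, the all-doses condition fails, and she is out of PP.
- Biopsy after dose 3 and before Week 36: all doses received, so she stays in PP as a non-responder. The protocol nowhere calls the biopsy a violation.

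Only the first group matters. In version 2.1 those are ad hoc biopsies, for example after a Day 0 Pap result suggesting cancer (6.12) or an unscheduled colposcopy on suspicion (6.13). Version 3.0 adds a Week 8 ThinPrep sample (Table 1), and its footnote says Pap smears are done on that specimen, so there is then a cytology reading between doses 2 and 3.

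**The plan's own figure.** Section 8.3 gives 165 subjects, 2:1, 40% versus 15%, 90% power and 90% evaluability; 8.9 tests at one-sided 0.025. The usual two-proportion formula gives 50 on placebo and 150 in all, and 150/0.9 = 167. At 165 × 0.9 = 148.5 evaluable subjects, power is 90.2%. The figure reproduces. These women stay in mITT as failures, so nothing here changes it.

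**Effect on PP.** Let p be an arm's response rate and q the share of that arm biopsied before dose 3. All of that share are non-responders, so dropping them gives

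PP rate = p / (1 − q).

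The documents give no q. The only related figure is 11 unscheduled biopsies (2.3) among 167 enrolled women (1.1.2) over the whole Phase 2b study: 11/167 = 6.6%. I assume q from 0 to 6.6% in each arm.

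| q active | q placebo | PP active | PP placebo | Difference (points) |
|---|---|---|---|---|
| 0 | 0 | 40.0% | 15.0% | 25.0 |
| 2% | 2% | 0.40/0.98 = 40.8% | 0.15/0.98 = 15.3% | 25.5 |
| 6.6% | 6.6% | 0.40/0.934 = 42.8% | 0.15/0.934 = 16.1% | 26.8 |
| 6.6% | 0 | 42.8% | 15.0% | 27.8 |
| 0 | 6.6% | 40.0% | 16.1% | 23.9 |

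Equal exclusion widens the difference by the factor 1/(1 − q). Exclusion in one arm only moves it in that arm's favour. With 110 and 55 women randomised, 6.6% is about 7 on active and 4 on placebo.

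Version 3.0 plans on 35% versus 14%. If its rules are unchanged, the same arithmetic moves 21.0 points to between 0.35 − 0.14/0.934 = 20.0 and 0.35/0.934 − 0.14 = 23.5.

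**The case against.** The strongest reply is that nothing is contradicted. Sections 6.13.2, 8.9 and 8.15 say how a woman is scored; 8.4 says who belongs to a supportive set. A PP set limited to women given the full regimen does what its name says, the primary population keeps these women as failures, PP exclusions are documented before unblinding, and disposition tables show doses received and reasons for stopping by arm. The literal part stands: the texts can all be obeyed at once. The consequence remains, because the dose was withheld on account of an event that is itself the failure. Documenting the exclusion blind hides the arm but does not undo selection on outcome, and 8.4 itself fixes the rule.

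A second reply is that retaining these women has its own asymmetry. Those who stop for adverse events, pregnancy or withdrawal stay out, so every incompletely dosed woman in PP would be a failure. That is true and is the price of the change. The distinction is that 6.13.2 ties the stop directly to non-response; the other reasons do not define an outcome.

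Third, the text is from version 2.1. Version 3.0 moves the primary analysis to intention-to-treat and counts missing data as failure. Its summary of changes lists no change to the PP definition or to the dosing stop, and its Section 2.1.3 still makes an interim tissue sample a non-response. Its Sections 6.13.2 and 8.4 are not shown, so whether the gap persists is unconfirmed.

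**Conclusion.** The point holds for version 2.1, limited to biopsies before dose 3. The supportive PP analysis excludes some early failures because they failed. The shift is probably small: from 25.0 points to between 23.9 and 27.8 over an assumed 0 to 6.6% excluded per arm. That upper value pools both arms, counts biopsies rather than women and covers the whole Phase 2b study, with neither timing nor arm reported. It is an assumption, not a bound on what happens before Week 12 in either arm.

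A reader might infer more, and the documents do not support it:

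- Not every woman biopsied before Week 36 leaves PP; those biopsied after dose 3 remain as non-responders.
- PP does not necessarily favour the active arm; the direction follows the arm with more early biopsies.
- The primary analysis, the success rule, the sample size and the power are untouched.

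This should be corrected, but it does not threaten the trial's main conclusion.

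**What to change.** Add to Section 8.4 of the current version: *Subjects whose dosing was stopped under 6.13.2 because of an unscheduled cervical biopsy before dose 3, who had received all doses due until then and have no other protocol violation, remain in the PP population as non-responders.*

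First check whether version 3.0 already says this. The cost is one sentence, and PP response rates become slightly less favourable in any arm with such women. No dosing or biopsy rule changes; only membership of the analysis set does.
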